15.2 Warnings and Precautions

Refer to Section 5 of the S8 Sinus Implant Package Insert.

15.3 Adverse Reactions

Adverse reactions from placement of the S8 Sinus Implant may include:

- Epistaxis
- Nasal discomfort
- Facial pain
- Headache
- Parosmia
- Nasal odour
- Eye irritation
- Dizziness
- Rhinalgia

- Presyncope
- Nasal congestion

Refer to Section 6.2 of the S8 Sinus Implant Package Insert for additional potential risks or adverse events.

Risks relating to the insertion and removal procedure

Risks associated with the insertion and removal of the S8 Sinus Implant are similar to those associated with other endoscopic sinus procedures. These potential risks include:

- Facial pain, nasal pain or discomfort related to the use of topical or local anesthetic medications
- Vasovagal reaction associated with the application of topical or local anesthetic medications
- Facial pain, nasal discomfort or pain, minor oozing or bleeding related to suctioning, manipulation of polyps, lysis of adhesions related to insertion or removal of the implant
- Injury to the middle turbinate or other structures of the middle meatus or ethmoid sinus
- Injury to nerves or blood vessels
- Infection at the insertion site
- Implant migration from its intended location in the sinus in which it was placed

15.4 Patient Counseling

For best results, subjects will be advised as follows:

- To use nasal saline sprays or irrigations
- That the implant is bioabsorbable and intended to soften over time. As the implant softens and polyps decrease, the implant may be expelled out of the nose on its own or with actions such as sneezing or forceful nose blowing.
- To call the study investigator immediately if they experience any of the following:
- Excessive nasal bleeding or symptoms of infection, such as excessive pain or discomfort, persistent headache, increased sinus discharge.
- Symptoms suggesting the implant has migrated posteriorly, such as irritation or choking sensation in the back of the throat.

15.5 Potential Benefits from Study Participation

There may be no direct benefits from participating in the study. However, study patients will undergo an enhanced level of clinical scrutiny compared to routine clinical care for chronic sinusitis, which may provide some indirect health benefits.

When placed in post-ESS patients with symptoms of recurrent nasal obstruction, the implant is intended to provide an immediate onset of action by dilating the sinus tissue, creating an opening in the middle meatus and ethmoid sinus, providing for ventilation, drainage and reducing the perceived sensation of nasal obstruction/congestion. The addition of mometasone furoate to the implant is intended to reduce inflammation and polyps. Patients may benefit from these actions.

16 STATISTICAL CONSIDERATIONS

A formal Statistical Analysis Plan (SAP) will be prepared prior to the study database lock and formal data analysis. Following is a summary of the intended analyses.

16.1 Sample Size Calculation

The 50-patient sample size was selected based on clinical judgment. Based on the RESOLVE II study (data on file at Intersect ENT Inc.), ~90% of sinuses had polyps of grade 1 or higher at Day 90. Based on this data, of the 100 sinuses that undergo implant placement at baseline, greater than 85 sinuses are expected to undergo repeat placements at Day 90. This will provide safety data on up to 185 implant procedures (100 implants at baseline; 85 implants at Day 90), which is deemed to be a large enough sample to detect potential additional implant-related adverse events associated with recurrent use of the implant.

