4 PROTOCOL SUMMARY

Study Title	The ENCORE Study: Safety Evaluation of Repeat Placement of the Corticosteroid-Releasing S8 Sinus Implant in Chronic Sinusitis Patients with Nasal Polyps
Objective	To assess the safety of repeat placement of the S8 Sinus Implant when used in chronic sinusitis (CS) patients with recurrent nasal polyps
Investigational Product	
The S8 Sinus Implant (mometasone furoate, 1350 mcg) is a bioabsorbable, corticosteroid-eluting implant studied for the treatment of nasal polyps in patients ≥ 18 years of age who have had ethmoid sinus surgery.
 
The S8 Sinus Implant is placed in the ethmoid sinus under endoscopic visualization. The implant may be left in the sinus to gradually release the corticosteroid over approximately 90 days. The implant must be removed by 90 days after placement or may be removed earlier at the investigator's discretion, using standard surgical instruments.

Study Design	
A prospective, non-randomized, open-label, multicenter clinical trial, consisting of three phases:
 
Screening
 
 • Patients who sign the institutional-review board (IRB) approved informed consent form will be considered enrolled into the study. • All consented subjects will undergo a screening assessment consisting of an endoscopic examination. 
Baseline/Procedure
 
 • Eligible subjects will undergo a baseline assessment. • Subject meeting all eligibility criteria will undergo an in-office bilateral placement of the S8 Sinus Implant in the ethmoid sinuses. 
Follow-up
 
 • Subjects will return for 7 follow-up visits at Days 30, 60, 90, 120, 150, 180 and 365. • At the Day 90 visit, subjects will undergo repeat in-office placement of the S8 Sinus Implant in each ethmoid sinus with nasal polyps (grade ≥ 1). Repeat placement will not be performed if polyp grade is < 1, or if the subject declines the procedure.
Subject Enrollment	A total of 50 subjects will be treated at up to 10 study centers across the U.S. with a maximum of 15 treated subjects at a single center.
Study Population	Patients ≥ 18 years of age with CS who have undergone prior endoscopic sinus surgery (ESS), including bilateral total ethmoidectomy, and present with bilateral ethmoid polyposis, and in whom bilateral placement of the S8 Sinus Implant is both feasible and medically appropriate.

[figure not shown]

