11.3 Follow-Up Phase

The follow-up period begins immediately post-procedure (once the patient exits the clinic). Each subject will return for up to 7 follow-up visits (*see Section 5 Study Flow Diagram and Section 6 Schedule of Assessments*).

- Day 30 (\pm 7 days)
- Day 60 (\pm 7 days)
- Day 90 (\pm 7 days) – implant removal & repeat implant placement
- Day 120 (\pm 7 days)
- Day 150 (\pm 7 days)
- Day 180 (\pm 14 days) – implant removal, as applicable
- Day 365 (\pm 14 days)

The protocol-required follow-up assessment at each visit through Day 180 will consist of:

- Nasal obstruction/congestion questionnaire,
- SNOT-22 questionnaire, and
- Endoscopic grading and video recording.

Repeat implant placement procedure at Day 90

At the Day 90 follow-up visit, subjects with ethmoid sinuses with polyps (grade ≥ 1) will undergo repeat implant placement unilaterally or bilaterally. Repeat implant placement must not be performed in the ethmoid sinuses with no nasal polyps (grade < 1). All implants placed at Day 90 must be removed at Day 180 or may be removed earlier at the investigator's discretion.

If polypectomy is performed at the Day 90 follow-up visit, polyp grading must be done after polypectomy to qualify a given subject for repeat placement of the S8 Sinus Implant.

Note: The assessment of symptoms and pregnancy testing must be performed before repeat implant placement procedure.

Unscheduled visits

Subjects may come in for additional unscheduled office visits if necessary. Circumstances that may warrant additional visits include but are not limited to:

- Worsening of sinus symptoms,
- Sinus-related adverse events requiring medical evaluation, and/or
- Implant migration

The assessment at an unscheduled visit will consist of:

- Nasal obstruction/congestion questionnaire,
- SNOT-22 questionnaire, and
- Endoscopic grading and video recording.

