16.4 Analysis of Other Endpoints

Implant delivery success rate

Implant delivery success rate will be reported with descriptive statistics. The left and right sides of each patient will be considered independent, and each patient is expected to contribute up to 4 observations: 2 implants at baseline; between 1 and 2 observations during follow-up (maximum of 1 repeat placements in each ethmoid sinus).

Interventions received

All interventions received for ethmoid sinus obstructions will be tabulated and reported with descriptive statistics.

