7.2 Sample Size

The 50-patient sample size was selected based on clinical judgment. In the RESOLVE II study, ~90% of sinuses had polyp grades ≥ 1 at Day 90. From this data, it is expected that of the 100 sinuses undergoing implant placement at baseline, greater than 85 sinuses would undergo repeat placements at Day 90. Therefore, a sample of 50 subjects will provide safety data on up to 185 implant procedures (100 implants at baseline; 85 implants at Day 90), which is deemed to be a large enough sample to detect potential additional implant-related adverse events associated with recurrent use of the implant.

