7.5 Safety Evaluation

Adverse events

All adverse events (AE) will be coded using the Medical Dictionary for Regulatory Activities (MedDRA). Where possible, and if applicable, AE will be localized to a sinus type and side.

The incidence and percentages of AE and serious adverse events (SAE) through Day 365, including treatment emergent AE (TEAE), implant-related AE and SAE, will be presented by MedDRA system organ class (SOC) and preferred term (PT). Complete patient listings of all adverse events will be provided. For each adverse event, the following will be specified:

- Start and stop dates, and event onset (study day)
- The affected side (right or left) if available
- Seriousness
- Severity
- Strength of relationship if available
- Action taken
- Outcome

In tables presenting implant-related AE, the incidences and percentages will also be presented based on two mutually exclusive periods of observation:

- from baseline to Day 90 (before repeat placement)
- from repeat placement (at Day 90) to Day 180

Concomitant medications

Prior and concomitant medications are coded to therapeutic class and PT using the World Health Organization (WHO) Drug Dictionary. All concomitant medications are listed and summarized in a table.

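### The sample-size text rests detection of recurrent-use adverse events on 185 procedures, but only about 85 to 90 are repeat placements, in about 43 to 50 subjects

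*Protocol*

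**What the plan says.** The sole objective (Protocol 8, SAP 2.0) is the safety of repeat placement. On size, Protocol 16.1 states: "The 50-patient sample size was selected based on clinical judgment". It cites a prior study in which about 90% of sinuses had polyps of grade 1 or higher at Day 90, and from this infers that, of 100 sinuses implanted at baseline, "greater than 85 sinuses are expected to undergo repeat placements at Day 90". The total is then given as "up to 185 implant procedures (100 implants at baseline; 85 implants at Day 90), which is deemed to be a large enough sample". SAP 7.2 repeats the argument and calls the total a "large enough sample to detect potential additional implant-related adverse events associated with recurrent use of the implant". Neither section names a target risk, a detection probability or a precision goal.

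Protocol 4 withholds the repeat placement if the polyp grade is below 1, "or if the subject declines the procedure". Protocol 11.3 adds that after a Day 90 polypectomy "polyp grading must be done after polypectomy to qualify a given subject for repeat placement". SAP 7.5 tabulates implant-related events in two separate periods, the second running "from repeat placement (at Day 90) to Day 180".

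For delivery success, Protocol 16.4 says: "The left and right sides of each patient will be considered independent, and each patient is expected to contribute up to 4 observations". SAP 7.4 reports the rate at Baseline, at Day 90 and for both combined, and allows an exact 95% interval for categorical measures where suitable.

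**The concern.** A first placement cannot produce an adverse event of recurrent use. Adding the 100 first placements to the repeats and calling the sum adequate for recurrent-use events credits the design with exposure it does not have. The 185 is the only figure offered in support of a clinically chosen N, and it bears on the only objective. If no new type of event appears after repeat placement, a reader who takes 185 as the denominator will think that a risk about half as large has been excluded as the repeat data can exclude.

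The count is also stated inconsistently. More than 85 repeats makes 185 a floor, whereas the total is given as a ceiling. The text does not explain the step from about 90% of 100 sinuses to a figure of 85.

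A smaller matter concerns the combined delivery rate. A subject can contribute up to four placements to it, so an exact binomial interval that treats them as independent is too narrow if outcomes within a subject are positively correlated.

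**Working it through.** **Reproducing the plan's figure.** 50 subjects × 2 sinuses = 100 first placements; 100 + 85 = 185, as stated. With the cited 90% at face value, 0.90 × 100 = 90 repeats and 100 + 90 = 190 in total.

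**Share that is repeat exposure.** 85/185 = 45.9%; 90/190 = 47.4%. The stated total over the repeats is 185/85 = 2.18.

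**Subjects with a repeat.** At most two repeats per subject: 85/2 = 42.5, so at least 43 subjects; 90/2 = 45. The maximum is 50.

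**What each count can show.** The documents give no target risk, so 1% and 2% are illustrations. The chance of at least one event is 1 − (1 − p)^n. The one-sided 95% upper bound after zero events is 1 − 0.05^(1/n).

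| Unit counted | n | Chance at p = 1% | Chance at p = 2% | Zero-event bound |
|---|---|---|---|---|
| All procedures | 185 | 84% | 98% | 1.6% |
| Repeat placements | 90 | 60% | 84% | 3.3% |
| Repeat placements | 85 | 57% | 82% | 3.5% |
| Subjects, all 50 | 50 | 40% | 64% | 5.8% |
| Subjects | 45 | 36% | 60% | 6.4% |
| Subjects, fewest | 43 | – | – | 6.7% |

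The placement rows treat placements as independent. The subject rows give risk per subject; they use a different unit and are not a further loss of information.

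**Combined delivery interval (secondary).** The documents give neither an intraclass correlation (ICC) nor an expected success rate, so both are assumed. Each subject's successes were taken as beta-binomial and convolved over 50 subjects, which gives exact coverage of the nominal 95% exact interval. Two layouts of 185 observations were used: 35 subjects × 4 + 15 × 3, and 42 × 4 + 1 × 3 + 7 × 2.

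| True success | ICC 0.1 | ICC 0.3 | ICC 0.5 |
|---|---|---|---|
| 95, 96, 97 and 98% | 92–94% | 85–87% | 78–82% |
| Every 0.1 point from 95 to 98% | 92–96% | 85–92% | 78–87% |
| 99% | 98% | 95% | 93% |

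Coverage moves up and down with the true rate, so the finer grid also reaches higher values. For the separate rates the lowest coverage from 95 to 99% success at ICC 0.1 / 0.3 / 0.5 is 95% / 93% / 91%, both at Baseline (50 subjects × 2) and at Day 90.

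**The case against.** The strongest reply is that nothing is concealed or miscalculated. The sentence itself prints the split into 100 and 85. It speaks of additional events, which needs something to compare with, and the first placements can be that reference. N rests on clinical judgment, with no power, bound or zero-event claim attached. SAP 7.5 already separates the period before the repeat from the period after it, and delivery success is also reported by time point.

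All of this stands and limits the point to the stated justification. It does not remove it. A reference adds nothing to repeat exposure, and the text sums the two and ties the sum to recurrent use.

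Three stronger readings are tempting, and the documents do not support them:

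- A reader might infer that 50 subjects is too few. No target risk is stated against which to judge that.
- A reader might infer that the safety analysis pools first and repeat placements. The two periods in SAP 7.5 show that the implant-related tables are also split.
- A reader might take a further loss off 85 for declines or dropout. The step from 90 to 85 may already be that allowance; the text does not say, so a second deduction could count it twice.

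On the delivery rate, Protocol 16.4 states its independence assumption openly and promises only descriptive statistics. The interval is optional, no success criterion depends on it, and every ICC above is assumed. Success may well be high, since a second attempt counts as success and unsuitable anatomy is excluded. At 99% the shortfall is small. That makes this part minor and conditional.

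**Conclusion.** The point holds as one about justification. Protocol 16.1 and SAP 7.2 support N with a procedure count about 2.2 times the repeat exposure relevant to the sole objective. The honest basis is about 85 to 90 repeat placements in about 43 to 50 subjects. With zero events, that excludes per-subject risks above about 5.8% to 6.7%, or per-placement risks above about 3.3% to 3.5% if placements are independent, against the 1.6% that 185 would suggest. The counts follow from the plan's own figures; the bounds are illustrations, because the plan states none. The floor and ceiling wording also conflicts. N, data collection and the SAP 7.5 tables are unaffected.

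The secondary point is minor. It applies only if an exact interval is shown for the combined delivery rate and outcomes within a subject are positively correlated. The loss of coverage is material at 95% to 98% true success with an ICC of 0.3 or more, and small near 99%.

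**What to change.** In Protocol 16.1 and SAP 7.2:

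- Keep 50 subjects and the clinical-judgment basis.
- Replace the 185 basis with the expected number of subjects receiving a repeat (about 43 to 50) and of repeat placements (about 85 to 90).
- Say whether these already allow for declines, regrading after polypectomy and dropout.
- If a detection limit is stated, lead with the per-subject bound and give the per-placement bound as assuming independent placements.
- Describe the 100 first placements as the reference.

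For delivery success, drop the independence statement in Protocol 16.4. In SAP 7.4, either report the combined rate without an interval, or give the proportion of subjects in whom every attempted placement succeeded, with an exact interval over subjects. The latter needs no estimated design effect. A design-effect adjustment would fail when there are no failures, which at 99% success happens in 20%, 28% or 37% of trials at ICC 0.1, 0.3 or 0.5. Exact intervals for the separate Baseline and Day 90 rates may stay, labelled as ignoring left-right correlation.

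The cost is wording in two sample-size sections, one deleted statement, one changed interval and one label, with no extra subjects or data. The downsides are a less favourable stated detection limit, and a delivery interval that is wider and describes subjects, not sinuses.

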16.2 Analysis of Safety Measures

The incidence of AEs and SAEs through Day 365, including treatment emergent AEs (TEAE), implant-related AEs, UADE/USDAE, and SAR/SUSAR will be presented.

16.3 Analysis of Efficacy Endpoints

Patient-reported outcomes

Symptom scores and change from baseline in symptom scores will be summarized using descriptive statistics. Means, standard deviations (SD), medians, ranges and, where appropriate, 95% CI for the mean assuming a normal distribution will be presented at each timepoint.

Endoscopic outcomes

Endoscopic grades and change from baseline in endoscopic grades will be summarized using descriptive statistics. Means, standard deviations (SD), medians, ranges and, where appropriate, 95% confidence intervals (CI) for the mean assuming a normal distribution will be presented at each timepoint.

16.4 Analysis of Other Endpoints

Implant delivery success rate

Implant delivery success rate will be reported with descriptive statistics. The left and right sides of each patient will be considered independent, and each patient is expected to contribute up to 4 observations: 2 implants at baseline; between 1 and 2 observations during follow-up (maximum of 1 repeat placements in each ethmoid sinus).

Interventions received

All interventions received for ethmoid sinus obstructions will be tabulated and reported with descriptive statistics.

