Implant delivery success	Successful deployment of the S8 Sinus Implant to the target site. Deployment is considered successful if the procedure concludes with a successful placement in the target sinus, even if a second attempt is required. Implant delivery success rate is calculated as proportion of successful deployments of the S8 Sinus Implant to the target site per total number of sinuses attempted including the baseline and repeat placement procedures.

Term	Definition
Malfunction	Failure of an investigational medical device to perform in accordance with its intended purpose when used in accordance with the instruction for use or clinical investigation plan. [BS EN ISO14155] Failure of a device to meet its performance specifications or otherwise perform as intended. Performance specifications include all claims made in the labeling for the device. The intended performance of a device refers to the intended use for which the device is labeled or marketed. [21CFR 803]
Nasal obstruction/congestion scale	A 4-point scale defined as follows: 0: No symptoms 1: Mild symptoms, clearly present but minimal awareness and easily tolerated 2: Moderate symptoms, definite awareness of symptoms that is bothersome but tolerable 3: Severe symptoms, hard to tolerate, cause interference with activities or daily living
Percent ethmoid sinus obstruction	Estimated visually based on endoscopic examination on a scale ranging from 0% (no obstruction) to 100% (complete obstruction of the ethmoid cavity by polyps, edema and/or scarring).
Polyp grading scale	Polyps are assessed endoscopically and graded on an 8-point scale ranging from 0 to 4 defined as follows: 0: No visible sinonasal polyps 1: Small amount of sinonasal polyps confined in middle meatus 1.5: Small amount of sinonasal polyps confined in middle meatus with expanded amount of polypoid edema obstructing $\geq 25\%$ of the ethmoid sinus cavity 2: Expanded amount of sinonasal polyps confined in middle meatus 2.5: Expanded amount of sinonasal polyps confined in middle meatus with expanded amount of polypoid edema obstructing $\geq 50\%$ of the ethmoid sinus cavity 3: Sinonasal polyps extending beyond middle meatus but not totally obstructing the nasal cavity 3.5: Sinonasal polyps extending beyond middle meatus with expanded amount of polypoid edema obstructing $\geq 75\%$ of the ethmoid sinus cavity 4: Sinonasal polyps extending beyond middle meatus and completely obstructing the nasal cavity

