6.6 General Statistical Procedures

Statistical summaries and confidence intervals (CI) are generated using SAS[®] software, version 9.4 or higher. Descriptive statistics are provided for all summarized data by displaying the mean, standard deviation (SD), median, minimum and maximum for continuous data, and the count and percentage for categorical data. Unless stated otherwise, a two-sided 95% CI is calculated when a CI is presented. A p-value < 0.05 is considered as statistically significant.

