7.4 Efficacy and Other Endpoints

Continuous measures are analyzed using descriptive statistics such as means, medians, and SD. and, where appropriate, 95% CI for the mean assuming a normal distribution.

Continuous measures include:

- Nasal Obstruction/Congestion score: Change from baseline to each time-point (Days 30, 60, 90, 120, 150, 180) in the mean score (scale 0 to 3)
- SNOT-22 score: Change from baseline to each time-point (Days 30, 60, 90, 120, 150, 180) in SNOT-22 total score, domain scores, and individual symptom scores. The total score of SNOT-22 is calculated as the sum of all items, and ranges from 0 to 110 with the highest score representing worsening. The following table lists corresponding items and ranges for each symptom domain.

SNOT-22 Domains	Survey Items	Score Range
Rhinologic Symptoms	#1, #2, #3, #6, #21, #22	0–30
Extra-Nasal Rhinologic Symptoms	#4, #5, #6	0–15
Ear/Facial Symptoms	#2, #7, #8, #9, #10	0–25
Psychological Dysfunction	#14, #15, #16, #17, #18, #19, #20	0–35
Sleep Dysfunction	#11, #12, #13, #14, #15	0–25

- Bilateral Polyp Grade: Change from baseline to each time-point (Days 30, 60, 90, 120, 150, 180) in bilateral polyp grade (scale 0 to 8), which represents a sum of left and right sides. The bilateral polyp grade for a given patient is set as missing if the grade for one side is missing.
- Percent Ethmoid Sinus Obstruction: Change from baseline to each time-point (Days 30, 60, 90, 120, 150, 180) in percent ethmoid sinus obstruction (scale 0% to 100%). Percent ethmoid obstruction scores on left and right sides are averaged for each subject at each time point. The results for a given patient is set as missing if the score for one side is missing.

Categorical measures are analyzed as counts, rates, proportions and frequencies. Where it is appropriate, 95% CI (computed using the exact method) and p-values will be presented.

Categorical measures include:

- Implant delivery success rate: Proportion of successful deployments of the S8 Sinus Implant to the target site per total number of sinuses attempted including the baseline and repeat placement procedures. Implant delivery success rate at Baseline, Day 90 and Baseline & Day 90 combined will be presented.

- Interventions received: Proportion of subjects who received interventions (i.e., sinus-related medications, systemic steroid interventions, and surgical interventions) through Day 365.

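### An exact 95% CI on the delivery success rate, if printed, would ignore clustering of about 185 placements within 50 patients and could be too narrow

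*Protocol*

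**What the plan says.** Protocol 16.4 sets the unit of analysis for delivery success: "The left and right sides of each patient will be considered independent, and each patient is expected to contribute up to 4 observations". The same paragraph says "Implant delivery success rate will be reported with descriptive statistics". Under Implant delivery success, Protocol Section 3 defines the denominator as "per total number of sinuses attempted including the baseline and repeat placement procedures".

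SAP 6.6 describes descriptive statistics as "the count and percentage for categorical data". SAP 7.4 introduces its list of categorical measures with "Where it is appropriate, 95% CI (computed using the exact method) and p-values will be presented". Delivery success is the first item on that list: "Implant delivery success rate at Baseline, Day 90 and Baseline & Day 90 combined will be presented".

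Protocol 16.1 and SAP 7.2 expect 100 placements at baseline and 85 at Day 90 from 50 patients. Neither document justifies the independence statement or provides a patient-clustered interval. Neither sets a hypothesis, threshold or performance goal for this rate.

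**The concern.** A count and a percentage need no independence assumption. The assumption matters only for an interval or a test, and SAP 7.4 leaves both possible for this endpoint. A programmer who takes the unit of analysis from Protocol 16.4 and the interval method from SAP 7.4 could reasonably print a Clopper-Pearson interval with n = 185.

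That interval requires independent trials. A patient's two sides share a visit, and each repeat placement goes into a sinus that was treated at baseline. Positive correlation is therefore plausible, although the documents do not give its size. What is at stake is the stated precision of a reported rate; the estimate itself does not change.

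**Working it through.** **Inputs from the documents.** There are 50 patients with two placements each at baseline, and 85 expected repeats (Protocol 16.1). The interval is a two-sided 95% exact CI (SAP 6.6 and 7.4). The denominator is sinuses attempted (Protocol Section 3).

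**Assumed inputs.** ICC 0 to 0.5; true success rate 95% to 99%; 35 patients with two repeats and 15 with one.

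**Step 1: the plan's count.** 50 × 2 = 100, and 100 + 85 = 185, as stated. That is 185/50 = 3.7 placements per patient. The assumed layout agrees: 35 × 2 + 15 × 1 = 85.

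**Step 2: design effect.** DEFF = 1 + (m − 1) × ICC, where m = Σk²/Σk and k is the cluster size.

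- Structure A, in which only the two sides within a procedure correlate: 50 + 35 = 85 pairs and 15 singles. m = (85 × 4 + 15 × 1)/185 = 355/185 = 1.92. At ICC 0.3, DEFF = 1.28 and the standard error ratio is √1.28 = 1.13.
- Structure B, in which all of a patient's placements share one correlation: 35 clusters of 4 and 15 of 3. m = (35 × 16 + 15 × 9)/185 = 695/185 = 3.76. At ICC 0.3, DEFF = 1.83 and the standard error ratio is √1.83 = 1.35.

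**Step 3: coverage of the unadjusted exact CI on the combined rate.** Successes per cluster are beta-binomial with mean p and the given ICC. Convolution over clusters gives the exact distribution of the total. Coverage is the probability of all totals whose Clopper-Pearson interval contains p.

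| Structure | ICC | p = 95% | 97% | 98% | 99% |
|---|---|---|---|---|---|
| either | 0 | 96.0 | 95.1 | 96.3 | 98.9 |
| A | 0.1 | 95.1 | 94.1 | 95.5 | 98.5 |
| A | 0.3 | 93.1 | 91.9 | 93.5 | 97.7 |
| A | 0.5 | 91.1 | 89.5 | 91.1 | 97.0 |
| B | 0.1 | 93.2 | 92.0 | 93.7 | 97.7 |
| B | 0.3 | 87.2 | 85.3 | 87.4 | 95.4 |
| B | 0.5 | 81.4 | 78.5 | 79.8 | 93.5 |

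The layout matters little. With 42 patients having two repeats, one having one and seven having none, the ICC 0.3 rows become 92.9/91.6/93.3/97.6 (A) and 87.0/85.0/87.2/95.3 (B).

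**Step 4: what an adjusted interval looks like.** Recompute the exact limits at an effective n of 185/DEFF.

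- 176/185 (95.1%): unadjusted 91.0–97.8%, width 6.8 points. With DEFF 1.28 (effective n 145): 90.3–98.0%. With DEFF 1.83 (effective n 101): 88.9–98.4%, width 9.5 points.
- 185/185: the lower limit is 98.0% unadjusted and 96.4% with DEFF 1.83. At the extreme of ICC 1 under structure B (DEFF 3.76) it is 92.8%.

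**Step 5: the separate rates.** These also pool two sides per patient. At ICC 0.3 and true rates of 90/95/99%, coverage is 92.2/96.3/96.5% at Baseline and 92.6/95.9/97.9% at Day 90. The issue is smaller there but not absent.

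**The case against.** The strongest objection is that the plan may contain no error at all. Protocol 16.3 names a 95% CI for the efficacy endpoints, whereas 16.4 gives delivery success descriptive statistics only, and SAP 6.6 defines those for categorical data as count and percentage. The CI sentence in SAP 7.4 covers several measures and is qualified. The table mock-ups in SAP Appendix B, whose content was not available here, may settle the matter. This stands: a CI is permitted, not promised.

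A reader might infer that the protocol also declares the Baseline and Day 90 placements independent of each other. It does not. The sentence names only left and right sides, and it can be read as a counting rule. Independence across procedures would enter only by putting both into one binomial interval. The larger losses (structure B) depend on correlation across procedures about 90 days apart, and the documents give no evidence for or against it.

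The ICC and true rate are assumptions, and there are reasons to expect few failures. Entry requires anatomy amenable to bilateral placement (Protocol 10.2), and a placement achieved on a second attempt counts as a success (Section 3). An ICC of 0.3 at a 98% rate is not trivial: after one failure, the chance of another rises from 2% to 0.02 + 0.3 × 0.98 = 31%.

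The denominator is also not fully settled. Protocol 16.6 and SAP 5.0 restrict analyses to sinuses that received an implant at baseline. Read literally, that would remove baseline failures. The working follows the endpoint's own definition, sinuses attempted.

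These points limit the size of the concern. They do not supply a reason to keep an unsupported independence statement beside an optional exact CI.

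**Conclusion.** This is a minor point, worth an inexpensive edit and held with medium confidence. If an exact CI is printed on the combined rate, its coverage at ICC 0.3 and true rates of 95–98% falls to about 92–93.5% (structure A) or 85–87% (structure B). At ICC 0.1 the ranges are 94.1–95.5% and 92.0–93.7%. At a 99% rate coverage stays at or above 95% up to ICC 0.3 under both structures, and at ICC 0 there is no loss. All of this rests on an ICC and a true rate that the documents do not give.

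A reader might go further and infer that the delivery rate is biased, or that the 185-procedure argument for the safety sample size fails. Neither follows. The point estimate does not depend on the correlation. The sample size is stated to rest on clinical judgment and on detecting adverse events, and no decision in the trial uses this rate. If only count and percentage are reported, nothing is wrong.

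Separately, "between 1 and 2 observations during follow-up" is a clerical slip. The Protocol Summary allows no repeat placement when the polyp grade is below 1 or the subject declines, so the count is 0 to 2. No result changes.

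**What to change.** Before database lock, amend SAP 7.4 as follows:

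1. Override the independence statement of Protocol 16.4 for this endpoint.
2. Report the Baseline, Day 90 and combined rates as count and percentage.
3. If any interval is shown, compute it with the patient as the cluster for all three rates, not only the combined one. A design-effect-adjusted exact interval is one option, and it can still be computed at 100% success. The ICC cannot be estimated when there are no failures, so the SAP should name the value or range to be used in that case.
4. Correct the follow-up count to 0 to 2 per patient.

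The proportion of patients with every attempted placement successful, with an exact CI on patients, is an optional addition that needs no ICC (50/50 gives a lower limit of 92.9%). It must be labelled as a different estimand that depends on the number of attempts. At a placement rate of 98% with no correlation it is 0.98² = 96.0% for two attempts and 0.98⁴ = 92.2% for four.

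The cost is an SAP sentence or two, no new data, and a somewhat wider interval (for 176/185, 9.5 points instead of 6.8 at DEFF 1.83).
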